Assessment of Learning Powered Mobility Use (ALP v. 2.0). 10 minutes or less to complete. The ALP is an observational performance assessment focused specifically on stages of learning and proficiency with powered mobility devices. The tool uses eight descriptive, behavior-based categories ranging from Novice to Expert across five performance domains, including Attention, Activity and Movement, Understanding of Tool Use, Expressions and Emotions, and Interaction and Communication. These eight categories are grouped into three learning stages: Explore Function (categories 1-3), Explore Sequence (categories 4-5), Explore Performance (categories 6-8). Members of the research team will observe each child participant in their natural setting for up to 10 minutes to identify a child's performance categories and learning stage during the three scheduled research visits. They will provide each family with associated ALP strategies for facilitating device use based on the learning stage of the child. This activity may be done during the scheduled in-person visits or remotely, and will be video-recorded for scoring by the research staff at a later time.

Daily driving log. Less than five minutes to complete. Caregivers will complete a daily driving log that indicates the date, time, and environment of Explorer Mini (A) or modified ride-on car use (B). Caregivers will also make notes about the child's enjoyment level and general activities while using each device. To supplement caregiver reported data, automated device use data such as frequency and duration of activation, average speed, and distance traveled, will be collected either via a custom data logger (mounted on the modified ride-on car) or through integrated device systems (built-in to the Explorer Mini) which allow designated users (in this case, members of the research team) to access device use data via mobile Apps and secure servers. Driving logs will be completed remotely.

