 - We do not anticipate the need to withdraw any participants involuntarily, however, in cases where significant and consistent emotional distress of the child or caregiver is observed by the researcher, this would warrant withdrawal from the study without consent. Because participants will be temporarily using a ride-on car and Explorer Mini Device, procedures for orderly withdrawal and removal of the devices will include: 1) written and verbal communication of set use periods for each device (8 weeks +/- 5 day grace period). Written or verbal communication of device drop off and removal plan (set date for device drop off and pickup, explain pickup and disinfection procedures).

10.9 Anticipated direct benefits to participants. If there are any direct research-related benefits that some or all individual participants are likely to experience from taking part in the research, describe them below:

Do not include benefits to society or others, and do not include subject payment (if any). Examples: medical benefits such as laboratory tests (if subjects receive the results); psychological resources made available to participants; training or education that is provided.

A direct benefit for participants will be to receive training, education, and trial use of two pediatric powered mobility devices.

(10.10) Return of individual research results.

In this section, provide your plans for the return of individual results. An "individual research result" is any information collected, generated or discovered in the course of a research study that is linked to the identity of a research participant. These may be results from screening procedures, results that are actively sought for purposes of the study, results that are discovered unintentionally, or after analysis of the collected data and/or results has been completed.

See the **GUIDANCE Return of Individual Results** for information about results that should and should not be returned, validity of results, the Clinical Laboratory Improvement Amendment (CLIA), consent requirements and communicating results.

a. Is it anticipated that the research will produce any individual research results that are clinically actionable?

"Clinically actionable" means that there are established therapeutic or preventive interventions or other available actions that have the potential to change the clinical course of the disease/condition, or lead to an improved health outcome.

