ID: STUDY00011386 Early Powered Mobility for Toddlers With Cerebral Palsy Using the Permobil® Explorer Mini and a Modified Ride-On Car

Statistical Analysis Plan Document Date: 12/1/2020

Statistical Design and Power

Data Analysis:

All statistical analyses will be conducted using SPSS (version 26.0 IBM, Armonk, NY). Descriptive participant characteristics (e.g., age, sex, race/ethnicity, CP subtype, GMFCS-level) will be summarized as categorical variables.

Aim 1: Developmental, activity and participation outcomes

Sample size justification: Since the current proposal is a pilot study, there are no previous data to conduct a power analysis on the potential change of developmental, activity and participation outcomes as a result of using different powered mobility devices.

Analysis for measures assessed in Aim 1 will include descriptive statistics. Data will be assessed for normality and symmetry. If normality assumptions are met, we will use parametric statistics to examine between- and within-subject effects. If assumptions are not met, we will use the non-parametric equivalent of the planned analyses. We will calculate three separate analyses to examine changes in_developmental, activity and participation outcomes. (1) Separate 2 (group: 1, 2) x 3 (time: T0, T1, T2) repeated measures MANOVAs will be calculated to determine between- and within-subject changes on mean scores of developmental, activity and participation outcomes. (2)_Stratification into low and high usage groups will occur based on mean device use data. We will use these stratified groups to run our analyses to determine if device use is related to developmental, activity and participation outcomes. Separate 2 (group: low usage, high usage) x 3 (time: T0, T1, T2) repeated measures MANOVAs will be calculated to determine between- and scores of developmental, activity and participation outcomes. Separate 2 (group: low usage, high usage) x 3 (time: T0, T1, T2) repeated measures MANOVAs will be calculated to determine between- and within-subject changes on mean scores of developmental, activity and participation outcomes. Post-hoc analyses (i.e. Bonferonni correction) will be used for the above analyses to control for the type I error rate and determine where the significant differences exist. (3) We will also use visual analysis to determine if clinically significant differences exist.

Aim 2: Use patterns (frequency, duration, environment) & families' perspective and experiences

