Sample size justification: A power analysis based on preliminary data was used to determine the number of participants (*N*) necessary to satisfy statistical assumptions for the current study. Power was calculated from the results of the total time (minutes) a modified ride-on car was used between two groups: (1) Families who received bi-weekly support via in-person researcher visits (Mean minutes = 1,060; SD = 783.8), and (2) Families who received no support throughout a 3-month intervention period (Mean minutes = 171.4; SD = 206.1). Beta was set at .80 and alpha at .05 to calculate *N* which is standard practice. Analysis indicates that a sample of 6 participants in each group (modified ride-on cars, Explorer Mini) will produce meaningful treatment differences. This power analysis is appropriate given our hypothesis that the Explorer Mini will be used more frequently and more often than a modified ride-on car based on design features. Also, the above power analysis from previous data is based on between-group differences whereas the current study will examine within-group differences of use patterns between devices, resulting in less variability and greater likelihood of observing differences, if differences exist.

95% confidence intervals and mean number of driving sessions, mean duration (minutes) of driving sessions, and summed total duration (minutes) of driving sessions will be summarized by device type. Variable distributions will be examined to (1) identify appropriate response variable distributions, (2) screen for outliers, and (3) characterize patterns of data missingness. If assumptions for parametric statistics are met, we will use parametric statistics to examine within-subject effects. If assumptions for parametric statistics are not met, we will use the non-parametric equivalent of the planned analyses. A 2

(group: 1, 2) x 2 (time: T1, T2) repeated measures MANOVA will be calculated to determine withinsubject changes on the dependent measures of the mean number of driving sessions, mean duration (minutes) of driving sessions, and summed total duration (minutes) of device use. Significant differences will be followed-up with appropriate post-hoc analyses such as the Bonferonni correction to control for the type I error rate and determine where the significant differences exist.

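### Aim 1 analysis (2) cuts continuously recorded device use into low and high groups in at most 18 children; a regression on continuous use would keep more information and give a slope

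*SAP*

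**What the plan says.** SAP, Aim 1, analysis (2): "Stratification into low and high usage groups will occur based on mean device use data". The aim is to see whether children who use the devices more fare differently on the Aim 1 measures, and the model is given as follows: "Separate 2 (group: low usage, high usage) x 3 (time: T0, T1, T2) repeated measures MANOVAs will be calculated". The only factors are usage group and time. On multiplicity: "Post-hoc analyses (i.e. Bonferonni correction) will be used for the above analyses to control for the type I error rate".

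Use itself is held on continuous scales. Besides the caregiver's daily log, Protocol 5.1 (Daily driving log) says that "automated device use data such as frequency and duration of activation, average speed, and distance traveled, will be collected". The Aim 2 analysis in the SAP treats use as a quantity, with the dependent measures "mean number of driving sessions, mean duration (minutes) of driving sessions, and summed total duration (minutes) of device use".

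Protocol 2.7 gives a maximum of 18 children. Protocol 2.2a admits children at any GMFCS level from I to V and children at risk for CP. In the SAP, GMFCS level appears only in the descriptive summary: "Descriptive participant characteristics (e.g., age, sex, race/ethnicity, CP subtype, GMFCS-level) will be summarized as categorical variables". For Aim 1 the SAP describes the study as a pilot without data for a power calculation.

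**The concern.** The question in analysis (2) is one of degree: do children who drive more change more? A low/high label treats a child just above the cut like the heaviest user, and a child just below it like one who hardly drove. With 18 children that loss matters, and the result is a difference between two loosely defined groups, not a change in score per unit of use that a later study could build on.

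The grouping rule is also not fully fixed. The word mean may describe the cut or each child's average use; on neither reading are cut and metric both settled. The Aim 2 analysis lists three use measures, and Protocol 5.1 has two sources (caregiver log and automated record). The SAP does not say which phase or device counts.

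A secondary matter is that children of widely differing motor severity are enrolled and analysis (2) has no severity term. T0 is a level of the time factor, so the starting score is represented. A rate of change that differs with severity is not.

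**Working it through.** The SAP states no figure for this analysis, so there is none to reproduce. Its one sample size calculation belongs to Aim 2. I use only the means and SDs given there, to set the spread of use.

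**Inputs**
- N = 18 (Protocol 2.7).
- Supported families: mean 1,060 minutes, SD 783.8, so CV = 783.8/1,060 = 0.74. Unsupported families: "Mean minutes = 171.4; SD = 206.1", so CV = 206.1/171.4 = 1.20.
- Three months taken as 91 days: 1,060/91 = 11.6 and 171.4/91 = 1.9 minutes per day.
- Assumed: log-normal use; true correlation r of 0.4 or 0.5 between use and T0-T2 change.

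**Information lost by a cut at the mean.** For log-normal use, sigma = sqrt(ln(1 + CV²)). The mean lies at sigma/2 on the standardised log scale, so the share labelled high is p = 1 − Φ(sigma/2). The information kept is the squared correlation between the label and use:
- linear in log minutes: φ(sigma/2)² / [p(1 − p)]
- linear in minutes: (1 − 2p)² / [CV² p(1 − p)]

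| | CV 0.74 | CV 1.20 |
|---|---|---|
| sigma; sigma/2 | 0.660; 0.330 | 0.946; 0.473 |
| p; p(1 − p) | 0.371; 0.233 | 0.318; 0.217 |
| Expected high users, 18p | 6.7 | 5.7 |
| Kept, linear in log minutes | 0.1427/0.2333 = 0.61 | 0.1273/0.2169 = 0.59 |
| Lost | 39% | 41% |
| Kept, linear in minutes | 0.0670/0.1275 = 0.525 | 0.132/0.314 = 0.42 |
| Lost | 48% | 58% |

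A median cut would label 9 children high, not about 6 or 7, so several labels depend on the reading of the rule.

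**Power at N = 18.** Each setting has 20,000 simulated trials at two-sided 0.05. The split is a t-test on T0-T2 change with a mean cut. The continuous model regresses T0-T2 change on the square root of minutes per day, adjusted for T0. The planned analysis is represented, for one outcome, by the 2-df test of low against high on the two phase changes.

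| True relation | Analysis | r = 0.4 | r = 0.5 |
|---|---|---|---|
| Graded | Mean split, total change | 21-25% | 29-38% |
| Graded | Continuous, T0-adjusted | 30-36% | 41-54% |
| Graded, even over phases | Planned 2-df test | 15-19% | 22-28% |
| Graded, all in one phase | Planned 2-df test | 24-31% | 35-47% |
| Step at mean use | Mean split | 29-30% | 45-46% |
| Step at mean use | Continuous, T0-adjusted | 24% | 38% |

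The graded rows span both CVs and both graded shapes. Compared setting by setting, the continuous model leads the planned test by only about 4-9 points if the effect falls in one phase, and by more if it accrues evenly. With two children at zero use, the continuous figure can fall to 27% / 39% for an effect linear in minutes, still above the split. For a step effect with two zero users, the split's lead grows to as much as 11 / 17 points.

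**Severity (correlations assumed).** With no true use effect and severity correlated 0.5 with both use and change, false positives are about 12% for the mean split, 9-10% for the planned test, 14-16% for continuous use without severity, and 5% once severity itself is added. At correlations of 0.3 the split and the continuous model both sit at about 6%.

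**The case against.** The strongest reply is that this is a pilot, that Aim 1 claims no power, and that continuous use does not rescue the question. With Bonferroni over five Bayley domains (alpha 0.01, an illustration), power for a relation linear in log minutes is 14-15% / 27-28% with continuous use and 9% / 15-16% with the split. That stands: the gain is in efficiency and a usable slope, not a decisive answer.

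The gain also depends on assumptions. The CVs come from earlier ride-on car data, not from use averaged over two devices. A step effect favours the split. The information losses are large-population figures; within samples of 18 the mean cut loses about 36-37% when the relation is linear in minutes. A T0-T2 change model does not use T1. All of this stands and belongs with the recommendation.

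Three stronger readings are tempting and not supported:
- **That no cut is given at all.** The SAP's wording may well mean a cut at the mean. What is open is the metric, source and period.
- **That severity confounds the use analysis.** The documents do not show that use varies with severity, and at correlations of 0.3 the effect is negligible. Continuous use without a severity term is in fact slightly more exposed than the split. Adjustment is only as good as the proxy: with severity correlations of 0.5, false positives are 7% if the proxy correlates 0.8 with severity and 9-10% at 0.6.
- **That the split discards 70% of the information.** That needs a median cut, CV 1.20 and a relation linear in minutes.

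**Conclusion.** The point holds as a cheap improvement in method. Analysis (2) turns a continuous exposure that the trial already records into two groups. For a graded relation this costs about 39-41% of the information (linear in log minutes) or 48-58% (linear in minutes), and roughly 9-16 points of power against a split on total change in matched settings without zero users. These figures rest on log-normal use, the preliminary CVs and assumed correlations of 0.4-0.5. Nothing in the documents posits a threshold effect that would favour the split. The unspecified metric alone would be a matter of missing detail, and severity is a secondary, hypothetical point. The crossover comparison of devices is not affected.

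**What to change.** In SAP Aim 1, replace the low/high MANOVA as the main form of analysis (2):

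1. For each listed outcome, regress T0-T2 change on mean minutes of use per day over both phases, adjusted for the T0 score.
2. Name one data source. Use minutes per day because Protocol 10.8 allows "set use periods for each device (8 weeks +/- 5 day grace period", so a phase can run 56 − 5 = 51 to 56 + 5 = 61 days.
3. Fix in advance a transform that allows zero use, such as the square root.
4. Report the slope with a 95% CI as an exploratory association, and keep the Bonferroni control over the listed outcomes.
5. Keep low and high groups as a descriptive display, T1 included, with metric and cut fixed in advance.
6. Beside it, show one sensitivity model with a single severity covariate chosen now. The T0 Bayley gross motor score is a candidate: Protocol 5.1 has all subscales assessed, whereas 2.2a ties GMFCS to a CP diagnosis. State that it adjusts only as well as it measures severity, and adds nothing where it is itself the T0 outcome.

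The cost is SAP wording; no new data are needed. The price is about 5-8 points of power if the true effect is a step at mean use (more with zero users), slightly more exposure to confounding in the model without severity, and no use of T1 in the main model. Precision stays low: with T0 in the model, 15 residual df remain and p < 0.05 needs a partial correlation of about 0.48. An observed 0.4 would have a 95% CI of about −0.10 to 0.74 (Fisher z, SE 1/√14).

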Research Design and Timeline: We will conduct our work using a mixed-methods, counterbalanced AB crossover design, where intervention A is use of the Explorer Mini, and intervention B is use of the modified ride-on car. All participants at all sites will undergo the same research procedures. Participants will receive both powered mobility interventions, and randomization into two groups at each site will occur to determine which intervention participants will receive first (Modified ride-on car: n = 3; Explorer Mini: n = 3). Three research visits will be scheduled during the study. Baseline assessment (T0) will consist of initial device training and safety checkoff, interview, and administration of outcome measures. Intervention phase 1 will take place for 8 weeks, followed by a mid-study assessment (T1) at which time interviews and outcome measures will be repeated and parent perception/satisfaction with device will be assessed. Training and safety checkoff on the second device will occur. No washout period between devices is indicated because both devices provide self-initiated mobility. Intervention phase 2 will take place for 8 weeks, followed by the final study assessments (T2), where devices will be removed from the participants' homes and a final set of interviews and outcome measures will be administered. During each 8-week study phase, the researchers will conduct two virtual check-ins with each family to answer questions and provide support and standard activity suggestions for device use (i.e. open exploration, switch/joystick play, goal-directed driving).

Equipment:

Modified Ride-On Cars. Commercially available, off-the-shelf, battery-operated rideon toy cars will be modified. *Switch activation*. Unmodified, a child uses their foot to press a pedal or their finger to press a small switch located on the steering wheel to activate the ride-on car which is difficult for young children with CP. Modifications of ride-on cars will include installation of an easy-to-press switch that has a large surface area and responds to a light touch for activation. *Seating support*. Common materials, such as PVC pipe, swimming kickboards, and Velcro will be used to build a

customized supportive seating system. Seatbelts are added in all cars, and fivepoint harnesses are available if needed for appropriate postural support. Cars

Figure 1. Child with CP using a modified ride-on car.

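### Aim 1 analysis (2) gives each child one usage group for the whole study, so the T0-to-T1 change is probably compared between groups defined partly by driving done after T1

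*SAP*

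**What the plan says.** The SAP lists three analyses under Aim 1. The second asks about device use: its purpose is "to determine if device use is related to developmental, activity and participation outcomes". Children are divided first: "Stratification into low and high usage groups will occur based on mean device use data". The groups then enter the model: "Separate 2 (group: low usage, high usage) x 3 (time: T0, T1, T2) repeated measures MANOVAs will be calculated". Bonferroni post-hoc comparisons follow, to locate any differences.

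The SAP does not give the averaging window, the unit of use or the cut point.

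Protocol 5.1 (Research Design and Timeline) fixes the order of events: "Intervention phase 1 will take place for 8 weeks, followed by a mid-study assessment (T1", and later "Intervention phase 2 will take place for 8 weeks, followed by the final study assessments (T2". The child changes device at T1.

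Protocol 5.1 (Dependent Measures, Aim 2) also shows that use can be placed in time: "Caregivers will complete a daily driving log that indicates the date, time, and environment" of use of each device. Automated device data supplement the log.

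**The concern.** A usage group in a 2 x 3 repeated measures model takes one value per child, and that value is held against the change from T0 to T1 as well as the change from T1 to T2. If the mean covers both phases, about half of the driving period that sets a child's group falls after T1. That driving cannot have influenced the T0-to-T1 change.

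The reverse path is open. A child who progresses more by T1 may drive more in phase 2 and so land in the high-usage group. The protocol contains a concrete route for this. Staff assess powered mobility learning at the visits, and "They will provide each family with associated ALP strategies for facilitating device use based on the learning stage of the child". This makes the path plausible; it says nothing about its strength.

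Two things are at stake. The analysis could report a use-related gain at T1 when early gain led to later use. It could also weaken a true phase 1 relation by mixing in use that had not yet happened. Keeping use continuous would not help, since a continuous 16-week mean (8 + 8 weeks) has the same fault.

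**Working it through.** The SAP has no figure to reproduce here: it states that no power analysis was possible for Aim 1. The 6 per group under Aim 2 does not bear on this point.

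**1. Does any single grouping fit both intervals?**
- Two-phase mean: includes phase 2 driving, so it does not match T0-to-T1.
- Phase 1 mean: matches T0-to-T1, but ignores the driving done between T1 and T2.
- Phase 2 mean: lies wholly after T1.

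None matches both. The problem is therefore in the model, not only in the missing definition.

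**2. Inputs for size**
- From the documents: 18 children (Protocol 2.7); two 8-week phases (Protocol 5.1).
- Assumed: normal use scores; a 9/9 split; phase 1 use unrelated to the T0-to-T1 gain; the T1-to-T2 gain independent; one outcome at a time.
- Assumed and varied: the correlation r between phase 1 and phase 2 use (0.2, 0.5, 0.8), and the correlation b between the T0-to-T1 gain and phase 2 use (0, 0.3, 0.5).

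**3. Wrong group for phase 1.** The two-phase mean correlates √((1 + r)/2) with phase 1 use. The share of children placed on the wrong side is arccos(√((1 + r)/2))/π.
- r = 0.2: arccos(0.775)/π = 22%, about 4 of 18
- r = 0.5: arccos(0.866)/π = 17%, 3 of 18
- r = 0.8: arccos(0.949)/π = 10%, about 2 of 18

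**4. Apparent difference in T0-to-T1 gain.** The two-phase mean correlates b/√(2(1 + r)) with the gain. A half-and-half split turns a correlation c into a high-minus-low difference of 2 × √(2/π) × c = 1.596c in large samples. At b = 0.5:
- r = 0.2: c = 0.5/√2.4 = 0.323, difference 0.52 SD
- r = 0.8: c = 0.5/√3.6 = 0.264, difference 0.42 SD

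Simulation at n = 18 gives 0.40-0.49 SD, slightly smaller as expected.

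**5. Rejection rates.** Use has no effect on outcome; 20,000 simulated trials per setting; ranges are over r.

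| Test | b = 0 | b = 0.3 | b = 0.5 |
|---|---|---|---|
| Group-by-time multivariate test | about 5% | 6-8% | 10-13% |
| T0-to-T1 t-test, unadjusted 5% | about 5% | 8-9% | 13-17% |
| T0-to-T1 contrast, Bonferroni over an assumed three contrasts (5%/3 = 1.7%) | about 1.7% | 3-4% | 6-8% |
| T0-to-T1 t-test, grouped on phase 1 use | about 5% | about 5% | about 5% |

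For T0-to-T2, an unadjusted test with the two-phase grouping rejects in about 9-10% at b = 0.5, so the reverse path also reaches that contrast.

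A separate run with a split at the mean and r of 0 or 0.5 gave 12-15% for the multivariate test and 15-21% for the unadjusted T0-to-T1 test at b = 0.5. The pattern does not depend on the 9/9 split.

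**The case against.** The strongest reply has four parts.

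*The window is not stated.* This stands. A reader might infer that the SAP commits to a 16-week mean, and the text does not say so. It is the natural reading, because use is recorded in both phases and no restriction is given. A phase 1 window would protect the T0-to-T1 comparison but move the mismatch to the next interval.

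*The SAP asks only whether use and outcome are related.* In the simulations early gain and later use really are correlated, so rejecting is a correct detection of some association. This stands in part. The rejections are false only if read as use preceding or producing gain. But a group-by-time result showing high users gaining more by T1 invites that reading, and the model gives no means of separating the two directions.

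*The 13-17% is not the rate of the planned procedure.* This stands. A reader might take it as the error rate of the plan; it belongs to an unadjusted t-test. The multivariate test and the Bonferroni contrast are closer to what the SAP describes, and their rates are lower. Relative to the nominal level, inflation remains in both.

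*Phase-specific use has its own costs.* This stands too. Averaging over both phases balances device across children, because every child uses both. Use in one phase does not: under Aim 2 the SAP expects more use of the Explorer Mini, so high phase 1 users would more often be children who started on it. And the 5% under phase 1 grouping holds only because the simulation has no common cause. Protocol 2.2 admits GMFCS levels I-V, and baseline ability may affect both use and gain.

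**Conclusion.** The concern holds as a fault in the stated model, conditional on the natural reading of the averaging window. One fixed usage group cannot match exposure to both outcome intervals. With a two-phase mean, the T0-to-T1 comparison is partly defined by later driving.

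The amount of bias is unknown. It depends on a progress-to-use correlation that neither document supplies, and with none there is no inflation. Under the assumptions above, correlations of 0.3 and 0.5 raise the group-by-time test from 5% to about 6-8% and 10-13%. The misplacement of about 10-22% of children for phase 1 does not depend on that correlation and weakens a true relation.

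A reader might go further and conclude that Aim 1 as a whole is compromised. The documents do not support that. Analysis (1) compares randomised sequences and does not use the usage groups. Analysis (2) is a non-randomised comparison in a study that the SAP calls a pilot. The change is worth making because it is cheap and alters what analysis (2) can be taken to show.

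**What to change.** In analysis (2):

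- Define use separately for each phase from the dated logs and device data, stating the unit and, if groups are kept, the cut point.
- Relate phase 1 use to the T0-to-T1 change and phase 2 use to the T1-to-T2 change. One model with two change rows per child can do this, with device and phase as terms and the score at the start of each interval as a covariate.
- Allow for the correlation between a child's two rows. They share the T1 score, so measurement error pushes that correlation negative; a simple random intercept cannot represent this.
- Do not use phase 2 driving to classify children for any comparison involving T1.
- If a 16-week mean is kept, apply it only to T0-to-T2 and report it as an association without direction, since early gain can still raise later use.
- Label analysis (2) exploratory.

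The cost is SAP wording and a small programming change. The downsides should be stated with the results: 8-week use is noisier than 16-week use; phase-specific use is partly entangled with device, and 18 children give little room to separate them; and confounding by baseline ability remains.

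### The Aim 2 figure of 6 per group does not give 80% power in a two-sided two-group comparison on the SAP's own inputs (68%; 8 per group are needed), and the justification should be restated for the 18-child crossover

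*SAP*

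**What the plan says.** The Aim 2 sample size justification in the SAP rests on total minutes of modified ride-on car use in two groups from preliminary data:

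- "Families who received bi-weekly support via in-person researcher visits (Mean minutes = 1,060; SD = 783.8")
- "Families who received no support throughout a 3-month intervention period (Mean minutes = 171.4; SD = 206.1")

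The error rates are given as "Beta was set at .80 and alpha at .05" to obtain the number of participants. The conclusion is "a sample of 6 participants in each group (modified ride-on cars, Explorer Mini"). The SAP adds that "the above power analysis from previous data is based on between-group differences", while the trial will compare devices within child, and it expects less variability as a result. It does not say which test the calculation used, whether it was one- or two-sided, how the two SDs were combined, or how large the preliminary groups were.

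The planned Aim 2 analysis is a 2 x 2 repeated measures MANOVA, with 95% confidence intervals for the usage summaries. For Aim 1 the SAP says that no data were available for a power analysis.

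Protocol section 5.1 randomises, at each site, "Modified ride-on car: n = 3; Explorer Mini: n = 3" to the device used first. Every child then uses both devices. Section 3.1 names two sites besides the home institution, and section 2.7 gives a maximum of 18 children.

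**The concern.** A sample size statement should be recoverable from its inputs under the test that will be used. Here the means, SDs, alpha and power are all printed, so the figure can be checked, and the usual two-sided calculation does not return 6. The label Beta makes matters worse: read literally, beta of .80 means 20% power.

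The figure also does not describe the trial. Three sites with 3 + 3 children give 9 per order and 18 in total, and no child belongs to only one device group. A reader cannot get from 6 per group to 18 children. Because this is the only power calculation in the plan, what is at stake is whether its 80% claim can be cited or relied on.

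**Working it through.** **Inputs (SAP, Aim 2 sample size justification).** Means 1,060 and 171.4; SDs 783.8 and 206.1; alpha .05; power .80 (reading Beta as power); equal groups.

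**Effect size.**
- Difference = 1,060 − 171.4 = 888.6 minutes.
- SD with equal planned groups = √[(783.8² + 206.1²)/2] = √[(614,342 + 42,477)/2] = 573.1.
- d = 888.6/573.1 = 1.551.

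**The plan's figure first.** For an equal-variance two-sample t test with n per group, power comes from the noncentral t distribution with 2n − 2 degrees of freedom and noncentrality d√(n/2). At n = 6 the noncentrality is 1.551 × √3 = 2.69, on 10 degrees of freedom.

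- One-sided 5% (critical value 1.812): 72.3% at n = 5 and 80.3% at n = 6. The smallest n for 80% is 6, as stated.
- The one-sided normal approximation gives n = 2 × [(1.645 + 0.842)/1.551]² = 5.14, which also rounds up to 6.

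**The same inputs, two-sided.** The critical value at n = 6 is 2.228.

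| n per group | t test, equal variance | Welch |
|---|---|---|
| 6 | 67.8% | about 61% |
| 7 | 75.9% | 70% |
| 8 | 82.2% | 77% |
| 9 | 87.0% | 83% |

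So 80% needs 8 per group, or 9 if equal SDs are not assumed. The Welch column is relevant because the SDs differ 3.8-fold (783.8/206.1). The Welch value at n = 6 is 60.4% by approximation and 60.6% to 60.7% by simulation. The two-sided normal approximation gives n = 2 × [(1.960 + 0.842)/1.551]² = 6.53, so 7, with 76.6% power at 6; it is optimistic at this size.

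**Other ways of combining the SDs.**
- Simple average of the SDs: (783.8 + 206.1)/2 = 494.95, d = 1.795. The two-sided t test then has 79.99% power at 6.
- Weighting by degrees of freedom with unequal preliminary groups. The sizes are not given; 4 v 7 is assumed for illustration. SD = √[(3 × 614,342 + 6 × 42,477)/9] = 482.8, d = 1.84, and two-sided power is 81.9% at 6.
- The larger SD alone gives 14 per group two-sided and 11 one-sided by t test.

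**Planned design, two-sided 5%, same inputs.**
- 9 per order, as a two-group test: 87.0%.
- 18 children as pairs. The SD of the within-child difference is √(783.8² + 206.1² − 2ρ × 783.8 × 206.1). The documents give no correlation ρ, so a range is assumed: ρ = 0 gives SD 810.4 and 99.2% power; ρ = 0.5 gives SD 703.8 and 99.9%; ρ = 0.7 gives SD 656.2 and over 99.9%.
- For comparison, 12 pairs have 93% at ρ = 0, and 6 pairs have 58% at ρ = 0 and 70% at ρ = 0.5.

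**The case against.** The strongest reply has three parts.

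**The one-sided origin is not documented.** This stands. The SAP states neither sidedness nor pooling, and two-sided routes can also reach 6: averaging the SDs gives 79.99%, and degrees-of-freedom weighting with suitably unequal preliminary groups gives over 80%. A reader might infer that only a one-sided test reproduces 6; the documents do not support that. These routes may explain the figure, but they do not justify it. With equal planned groups, the variance of the difference in means is (783.8² + 206.1²)/n whatever the preliminary group sizes were, so 573.1 is the SD that applies. The directional hypothesis that the Explorer Mini will be used more would suit a one-sided calculation, but no one-sided test is planned.

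**A two-group t test is not the planned analysis.** This also stands, and the SAP says so itself. The 68% corrects the SAP's own calculation; it is not the power of the within-child MANOVA. Equally, the appeal to lower within-child variability does not support the figure 6, since no correlation or paired calculation is given.

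**Nothing practical turns on it.** This is largely right. A reader might infer that the SAP supports stopping at 12 children with too little power. The documents contain no such provision: the protocol gives a maximum of 18, and each child contributes both devices. Even 12 pairs would have at least 93% power at correlations of 0 or above (assumed).

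**Conclusion.** The concern holds as an error in the justification. With two equal groups and the printed means and SDs, a two-sided 5% test has about 68% power at 6 per group (61% by Welch), some 12 points below the stated 80%, and 80% needs 8 per group (Welch 9). Two-sided is the appropriate standard because MANOVA F tests are non-directional and the planned intervals are 95%. That 6 came from a one-sided t test is a plausible inference, not a documented fact.

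The result does not show that the trial is underpowered for the difference the SAP assumes: two-sided power is 87% with 9 per order as a two-group test and about 99% or more for 18 pairs. These figures assume normal data, all 18 children completing, no allowance for dropout or period effects, the preliminary SDs carrying over to the two devices, and a correlation of 0 or above. They say nothing about whether a contrast between supported and unsupported families is a sound guide to a difference between devices, which is a separate question.

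**What to change.** Amend the Aim 2 sample size justification in the SAP:

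1. Replace Beta with power in the statement of error rates.
2. State the test, its sidedness and how the SDs were combined.
3. Restate the result, for example: *On the pilot inputs, a two-sided 5% two-group test has 68% power with 6 per group (61% without assuming equal SDs), and 80% needs 8 (9) per group.*
4. Base the justification on the actual design: 18 children, 9 per order, each using both devices. Give the two-sided paired power with its assumed correlation range, for example 99% or more for 18 pairs at correlations from 0 to 0.7.

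The cost is SAP wording only. The figure for 6 per group becomes less favourable; enrolment, procedures and the planned analysis do not change.
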